3. STUDY DESIGN

We will accomplish the aims by a randomized controlled trial of 240 Jewish and Arab women (>18 years) who have been diagnosed with BC and have completed chemotherapy, recruited in Israel and randomized to undergo an 8-week (1.5 hours per week) program of group Art Therapy compared to women who will be designated to an 8-week sham Art Therapy group. We chose this design to be able to isolate and examine emotional processing and the effect of enhancing emotional processing on HRV and inflammatory cytokines and examine how these may mediate the effect of art therapy on depressive symptoms, pain and fatigue.

The primary outcomes are emotion processing, comprised of emotion awareness, expression and acceptance and the cholinergic anti-inflammatory pathway, comprised of resting HRV and inflammatory (pro and regulatory) cytokines. The secondary outcome measures are depression, pain and fatigue.

The study will take place at the cancer centers of 3 study sites: Rabin Medical Center, Rambam Medical Center and Ziv Medical Center, the enrollment period will vary until each cohort is collected and is expected to be approximately a month or a month and a half.

The interventions will be administered by an experienced Art Therapist who will be trained in this specific protocol by the PI [name] who is an Art Therapy [name] intervention is designed to follow the Bodymind model of AT⁶². Each session will start with a ten-minute rapport building and touching base and continue with 50 minutes of art making in a calm and supportive environment. Art materials are on the table and after the art therapist provides a brief explanation of the use of the materials; participants are encouraged to explore and experience as they wish. The art therapist is present to guide and assist. Participants are encouraged to minimize conversation; instrumental music is played to encourage introspective experiences. The session ends with 30 minutes of processing and discussion in which each participant shares and briefly presents their work and group participants can respond and or provide support.

The comparison group will meet for a half an hour. The interventionist will encourage the participants to color prefabricated shapes for 30 minutes. The same art materials as in the intervention group will be on the table as will the same instrumental music. We will not be controlling for the whole 90 minutes of the intervention group as are concerned that comparison group participants will become bored and this will defeat the purpose of the comparison group. The detailed role of the interventionist is described in section 5.2, and it is tailored to ensure optimal opportunities for participants to engage in emotional processing in a supportive environment.

The interventionists of both groups will keep scores that will be rated by the PI against the treatment manual to ensure fidelity (see Table 2).

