6.2.2 Enrollment, Baseline, and/or Randomization

Enrollment

Enrollment date is considered immediately following the signing of the consent form after which the enrollment date is recorded in the case book. The participant will be scheduled for a baseline visit in which she will be requested to fill out the baseline questionnaires and provide half an hour of baseline HR and Respiration measurements and 10 ccs of blood. Following this session, the participant will be randomized to the intervention or comparison group.

Baseline Assessments Visit 1 day 0- can be split in to 2 visits to reduce patient burden (see study schema- figure 1)

T1A

DEMOGRAPHICS AND TRADITIONALISM

- A.** We will be collecting baseline demographic data (age, marital status, children (if yes, and how many), religion, religiosity, education, employment, residence (city, village, etc).
- B.** We will measure ethnocultural differences using the Portrait Values Questionnaire (PVQ-RR), which is a 57-item scale consisting of items designed to measure 19 cultural values⁴³. The scale has been validated in 15 samples across 10 countries (n=6059) including Israel. The mean Cronbach α for the tradition values (which we will use as a covariate to enrich the ethno-cultural differences between Jews and Arabs, was 0.8343.

C. CHOLINERGIC ANTI-INFLAMMATORY PATHWAY

A. HRV: 20 minutes of resting ECG data will be recorded. The participants will be given instructions not to drink coffee or smoke for several hours before the lab visit as well as to sit quietly without talking or moving during the ECG recording.

B. Inflammation: We will collect 10 cc's of blood in order to measure immune dysregulation (pro-inflammatory cytokines IL-6, IL-8, IL-1 β , TNF- α), anti-inflammatory (IL-4, IL-10) and regulatory cytokine (TGF- β).

D. PATIENT REPORTED OUTCOMES (PRO):

A. Depression: The **Center for Epidemiologic Studies-Depression (CES-DR)** scale^{71- 10} ITEM SCALE.

B. Fatigue will be assessed using the Fatigue Symptom Inventory (**FSI**)⁷².

C. Pain: The **Breast Cancer Prevention Trial (BCPT) Symptom Scales**⁷³. The **PROMIS Pain Impact Scale**⁷⁴ measures how much pain interfered with different aspects of life in the past 4 weeks.

T1B

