A. The **Levels of Emotional Awareness Scale** is a written performance index of variation in the differentiation and complexity of emotional words used to answer the question “how would you feel and how would the other person feel” when presented with 10 evocative scenarios⁷⁵.

B. **Emotional Approach Coping** scales (e.g., **emotional processing, emotional expression**⁷⁶) and **COPE avoidance-oriented coping** subscales (e.g., denial, mental disengagement⁷⁷), all completed with reference to women’s experience of breast cancer.

C. The **Acceptance of Emotions Scale** assesses the extent to which subjects are accepting and nurturing toward their feelings²⁶.

B. Fatigue will be assessed using the Fatigue Symptom Inventory (**FSI**)⁷².

Randomization

Randomization will occur immediately following the baseline visit which will occur within 14 days of the screening visit and one week before the intervention begins. The University statistician will generate numbered envelopes to be opened consecutively as subjects enroll and the envelopes will designate individuals to the intervention through use of a random numbers table.

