6.2.4 T 2 – POST intervention

EMOTION PROCESSING

A. The **Levels of Emotional Awareness Scale** is a written performance index of variation in the differentiation and complexity of emotional words used to answer the question “how would you feel and how would the other person feel” when presented with 10 evocative scenarios ^{75,78}.

B. **Emotional Approach Coping** scales (e.g., **emotional processing, emotional expression** ^{79,80}) and COPE **avoidance-oriented coping** subscales⁷⁹ (e.g., denial, mental disengagement), all completed with reference to women’s experience of breast cancer.

C. The **Acceptance of Emotions Scale** assesses the extent to which subjects are accepting and nurturing toward their feelings²⁴.

D. PATIENT REPORTED OUTCOMES (PRO):

A. Depression: The **Center for Epidemiologic Studies-Depression (CES-DR)** scale^{71- 70} ITEM SCALE.

B. Fatigue will be assessed using the Fatigue Symptom Inventory (**FSI**)⁷².

C. Pain: The Breast Cancer Prevention Trial (BCPT) Symptom Scales⁷³. The PROMIS Pain Impact Scale⁷⁴ measures how much pain interfered with different aspects of life in the past 4 weeks.

CHOLINERGIC ANTI-INFLAMMATORY PATHWAY

A. HRV: 20 minutes of resting ECG data will be recorded. The participants will be given instructions not to drink coffee or smoke for 3 hours before the lab visit as well as to sit quietly without talking or moving during the ECG recording.

B. Inflammation: We will collect 10 ccs of blood in order to measure immune dysregulation (pro-inflammatory cytokines IL-6, IL-8, IL-1 β , TNF- α), anti-inflammatory (IL-4, IL-10) and regulatory cytokine (TGF- β).

T3-8 WEEKS AFTER END OF INTERVENTION Completion/Final Evaluation

CHOLINERGIC ANTI-INFLAMMATORY PATHWAY

A. HRV: 20 minutes of resting ECG data will be recorded. The participants will be given instructions not to drink coffee or smoke for 3 hours before the lab visit as well as to sit quietly without talking or moving during the ECG recording.

B. Inflammation: We will collect 10 ccs of blood in order to measure immune dysregulation (pro-inflammatory cytokines IL-6, IL-8, IL-1 β , TNF- α), anti-inflammatory (IL-4, IL-10) and regulatory cytokine (TGF- β).

D. PATIENT REPORTED OUTCOMES (PRO):

A. Depression: The **Center for Epidemiologic Studies-Depression (CES-DR)** scale^{71- 10} ITEM SCALE.

B. Fatigue will be assessed using the Fatigue Symptom Inventory (**FSI**)⁷².

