**NCT03377816: The Role of Emotional Processing in Improving the Quality of Life of
Breast Cancer Patients (REPAT)**

Statistical Analysis Plan- September 14th, 2017

The following statistical analysis plan was written in September of 2017 as part of the grant proposal for the REPAT study and was incorporated into the study protocol and guided the design of the actual study.

C.5 Statistical Methods:

C.5.1 Sample Size: A power analysis was conducted via Monte Carlo simulation in Mplus showed that a sample size of 240 (120 per condition), provides: (1) >90% power to detect a moderate effect size (Cohen's $d = 0.50$) of treatment on mechanisms, (2) >90% power to detect a moderate association ($r = 0.30$) between mechanisms and symptoms, and (3) >90% power to detect an indirect effect from treatment to symptoms via mechanisms. The sample size will also provide >80% power to detect a moderate effect size for the Condition by Ethno-Cultural group interaction.

C.5.2 Data Analysis: Prior to testing hypotheses, we will produce a thorough descriptive profile of the sample and examine the distributions of key variables involved in the hypotheses. We will also examine levels of nonresponse and **missing data**. Prior experience indicates attrition will be low; although, some missing data are expected due to missed assessments and dropout. Data will be analyzed using full information maximum likelihood to address missing data, supplemented with pattern-mixture modeling for non-random missingness. The first part of Hypothesis 1: women in the AT group experience greater increases in emotion processing, HRV, and regulatory cytokine levels and greater decreases in pro-inflammatory cytokines than women randomized to the Mandala condition will be tested using linear mixed models¹²⁹. Models will include a Time x Condition interaction to test whether the change over time in emotion processing and cholinergic anti-inflammatory processes is significantly different between treatment groups.

A significant interaction will be followed up by simple slope tests to characterize the degree of change separately in the AT and Mandala conditions.

The second part of Hypothesis 1: emotion processing and cholinergic anti-inflammatory processes mediate the effects of AT on symptoms (depression, pain, fatigue) will be tested using path analysis.

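### The primary outcomes span about 9 to 14 measures, and the SAP gives no significance level, composite, multiplicity control or success rule for testing them under Hypothesis 1

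*Protocol*

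**What the plan says.** Protocol section 3 makes two constructs primary: "The primary outcomes are emotion processing, comprised of emotion awareness, expression and acceptance and the cholinergic anti-inflammatory pathway", the latter "comprised of resting HRV and inflammatory (pro and regulatory) cytokines". No single measure is named as the primary endpoint.

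Sections 6.2.2 and 6.2.4 give the measures:

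- **Awareness:** the Levels of Emotional Awareness Scale, a "written performance index of variation in the differentiation and complexity of emotional words".
- **Coping:** the Emotional Approach Coping scales ("emotional processing, emotional expression") and COPE avoidance subscales, with "denial, mental disengagement" as examples.
- **Acceptance:** the Acceptance of Emotions Scale.
- **HRV:** resting HRV. Protocol section 2.5 narrows the hypotheses to high-frequency HRV.
- **Cytokines:** four that are pro-inflammatory ("pro-inflammatory cytokines IL-6, IL-8", IL-1β and TNF-α), and then "anti-inflammatory (IL-4, IL-10) and regulatory cytokine" TGF-β.

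SAP C.5.2 describes the analysis of the first part of Hypothesis 1: "Models will include a Time x Condition interaction to test whether the change over time in emotion processing and cholinergic anti-inflammatory processes" differs between the groups. The hypothesis is directional: emotion processing, HRV and regulatory cytokines should rise more with art therapy, and pro-inflammatory cytokines should fall more. SAP C.5.1 claims more than 90% power for d = 0.50 on mechanisms with 240 women, 120 per condition.

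**The concern.** The treatment effect on mechanisms is the trial's main claim. The plan offers many measures on which to show it and does not say how many must succeed, in what order they are tested, or at what level. Nothing in the SAP would stop one significant cytokine out of seven from being reported as support for Hypothesis 1. The plan also leaves open whether measures are modelled singly or combined, so that choice could be made after the results are known.

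The same measures then act as mediators for three symptoms. Taken singly, 9, 11 or 14 mediators give 27, 33 or 42 indirect effects, again with no stated control.

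**Working it through.** **Inputs from the documents:** 240 women, 120 per condition, d = 0.50, power above 90% (SAP C.5.1); 15% attrition and a target of 300 (Protocol, Sample Size and Population).

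**Assumptions:** two-sided 5% per test, because the only related figure in the SAP is the 95% interval for bootstrapped indirect effects; one model per measure; any one success counts; correlations between test statistics, for which the documents give no values.

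**1. The plan's own power.** With a two-sample t-test, the non-centrality is d × √(n/2) = 0.5 × √60 = 3.87. At two-sided 5% the critical value is 1.97 on 238 degrees of freedom, and power is 97%. This agrees with the claim of more than 90%, but for one unadjusted comparison.

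**2. Counting the measures.**

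- Strict reading of section 3: awareness, expression, acceptance, HRV, four pro-inflammatory cytokines and TGF-β. 3 + 1 + 5 = 9.
- Adding IL-4 and IL-10, which section 6.2.2 labels anti-inflammatory: 11.
- Adding the emotional-processing coping scale and the two COPE avoidance subscales given as examples: 14.

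**3. Chance of at least one false positive with all nulls true.** For independent tests this is 1 − 0.95^k, for example 1 − 0.95^11 = 43.1%. For correlated tests it comes from numerical integration over equicorrelated normal statistics.

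| Measures | Independent | Correlation 0.3 | 0.5 | 0.7 |
|---|---|---|---|---|
| 9 | 37% | 33% | 27% | 20% |
| 11 | 43% | 37% | 30% | 22% |
| 14 | 51% | 44% | 35% | 25% |

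**4. Other readings of the plan.**

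- Two domain-level tests: 1 − 0.95² = 9.8%.
- Four quantities as Hypothesis 1 names them (emotion processing, HRV, regulatory cytokines, pro-inflammatory cytokines): 1 − 0.95⁴ = 18.5%.
- Only errors in the hypothesised direction count, independent tests: 1 − 0.975^11 = 24% and 1 − 0.975^14 = 30%, against 2.5% for a single test.
- All measures must succeed: no inflation.

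**5. Power with control, d = 0.50, same t approximation.** The column for 204 takes 15% attrition from 240 (240 × 0.85 = 204); its non-centrality is 0.5 × √51 = 3.57.

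| Level per test | 240 analysed | 204 analysed |
|---|---|---|
| 0.05/9 (Holm, first step) | 86% | 78% |
| 0.05/11 | 84% | 76% |
| 0.05/14 | 82% | 73% |
| 0.025 (two composites) | 95% | 90% |

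If instead 300 are randomised and 15% lost, 300 × 0.85 = 255 remain, and power at 0.05/11 is 87%.

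**The case against.** A reader might infer that the SAP tests at least 11 measures separately at 5%, so that the main claim carries a false-positive risk of one in three to one in two. The documents do not support that as fact:

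- No significance level is stated for the mixed models.
- The SAP refers to mixed models in the plural but does not say whether measures are modelled singly or combined, and the objectives speak of two mechanisms.
- Eleven is not a floor. Section 3 and Hypothesis 1 name only pro-inflammatory and regulatory cytokines, which gives nine measures. For the same reason, 33 indirect effects is not a minimum.
- The 51% needs 14 independent tests, including avoidance subscales outside the three named components.
- Hypothesis 1 is worded as a conjunction. If every part must succeed, there is no inflation.

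All of this stands. It limits the figures to conditional illustrations, but it does not supply the missing rule, because the documents never adopt the conjunctive reading or define a composite.

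It can also be said that a mechanistic study needs less formal error control. That bears on the choice of remedy. A listed primary set with a stated success rule might be enough without Holm. It does not excuse having no rule, because here the mechanism claim is the primary claim.

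**Conclusion.** The point holds as a gap in specification. The primary outcomes cover about 9 to 14 measures, and neither document gives a significance level, composite, ordering, adjustment or success rule for the Hypothesis 1 tests.

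The size depends on how the gap is filled. With separate two-sided 5% tests and any one success counting, the risk of at least one false positive is 43% for 11 independent measures. It is 27% to 51% over 9 to 14 measures with correlations of 0 to 0.5, and 20% to 25% at correlation 0.7. With two to four independent aggregated tests it is 10% to 19%. With an all-must-succeed rule it is not inflated. The level, the correlations and the any-one-counts rule are assumptions.

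The claim of more than 90% power is met by a single unadjusted test, but not by a Holm first step over 9, 11 or 14 measures.

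**What to change.** In SAP C.5.2, list the primary measures by name, including whether IL-4, IL-10, the emotional-processing scale and the avoidance subscales belong. State two-sided 5%, and apply Holm across the Time x Condition tests of that list. Treat other measures and the mediation paths as exploratory, with unadjusted 95% intervals. State what pattern of results counts as support for Hypothesis 1.

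Alternatively, test one composite per domain at 2.5% each, and test components only if their composite is significant. Signs and weights must be fixed in advance, because the hypothesis expects HRV and regulatory cytokines to rise and pro-inflammatory cytokines to fall.

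Either choice should be settled before any outcome comparison by arm, since Protocol section 9.3.2 plans two interim analyses.

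**Cost.** Only wording changes, but SAP C.5.1 should restate power:

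- **Holm:** about 86%, 84% and 82% at the first step for 9, 11 and 14 measures with 240 analysed, or about 73% to 78% with 204.
- **Composites:** 95% (90% at 204), but only if d = 0.50 applies to the composite itself. At a composite d of 0.40, power at 2.5% is about 80% with 240 and 72% with 204. An effect on one component is diluted.
- **Mediation:** it loses confirmatory standing, although the SAP places it within Hypothesis 1.

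These figures use a simple two-sample approximation. The restated power should come from the planned mixed model.

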4. SELECTION AND ENROLLMENT OF PARTICIPANTS

We will accomplish the aims by recruiting 240 Jewish and Arab Women (>18 years) who have been diagnosed with breast cancer and have completed chemotherapy and are still undergoing some form of treatment, to include adjuvant treatment or within 5 years of completing chemotherapy, surgery and/ or radiation therapy. There is evidence that elevated depression, anxiety, fatigue and pain continue over 5 years of survivorship. We plan to recruit 50% Jewish women and 50% Arab women (30% more than represented both in general society and in the cancer population), for comparison. We plan to identify and approach women as they come in for their simulation visit to Radiation Oncology as this usually occurs about a week before radiation therapy starts and will be a good time to obtain baseline measures, however each site nurse will have the freedom to recruit patients who fit the enrollment criteria at other stages of treatment, after chemotherapy. The site nurse will be in charge of identifying and recruiting appropriate candidates for the trial and will use a screening log in order to document reasons for ineligibility or non-participation for eligible candidates.

4.1 Inclusion Criteria

1) adult (>18) females with initial or recurrent BC; 2) study entry within one year of diagnosis and 3 months after adjuvant cancer care (chemotherapy and radiotherapy (RT)) or reconstructive surgery; any additional or replacement standard medical treatment for cancer is allowed (i.e., surgery, chemotherapy, radiotherapy, neo-adjuvant chemotherapy, endocrine therapy); 4) additional medication is allowed, excluding what is described in exclusion criteria, and will be assessed for potential inclusion as a covariate; 5) can complete assessments in Arabic or Hebrew; 6) provides informed consent.

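### The protocol gives two outer entry windows, five years after treatment (section 4) and one year after diagnosis (4.1), and its main recruitment visit fits 4.1 poorly

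*Protocol*

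**What the plan says.** Protocol section 4 describes women who "have completed chemotherapy and are still undergoing some form of treatment" or, as an alternative, are "within 5 years of completing chemotherapy, surgery and/ or radiation therapy". It supports the longer window by noting that symptoms persist over five years. For recruitment, the plan is to "identify and approach women as they come in for their simulation visit to Radiation Oncology", a visit placed "about a week before radiation therapy starts and will be a good time to obtain baseline measures". It adds that "each site nurse will have the freedom to recruit patients who fit the enrollment criteria at other stages of treatment, after chemotherapy".

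Protocol section 4.1, criterion 2, sets the entry time as "study entry within one year of diagnosis and 3 months after adjuvant cancer care (chemotherapy and radiotherapy (RT)) or reconstructive surgery". The sentence goes on to allow other standard cancer treatment, and its examples include both chemotherapy and radiotherapy.

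Section 5.3.1 repeats that list of allowed treatments, then says that participants should not receive chemotherapeutic agents during the study. Section 3 says only that chemotherapy has been completed and gives no time window. The phone screen in 6.2.1 covers age, stage and language. The SAP does not define the population.

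**The concern.** Section 4 and section 4.1 give different answers for the same woman, and nothing in the protocol ranks one above the other. Three sites screen against these texts, so they may enrol different populations in good faith.

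The timing also touches the outcomes. Section 6.2.2 places baseline one week before the intervention. If a woman is approached at simulation and has her baseline then, radiotherapy would begin at about the first session, between the baseline (T1) and post-intervention (T2) measures of cytokines, heart rate variability and fatigue. A woman recruited years after treatment has no such exposure in that interval. Randomisation is stratified by site, ethnicity and traditionalism (section 8.2), not by treatment phase. The only covariate that the SAP names is traditional values, under Hypothesis 3. Sections 4.1 and 4.2 mention medication, recent illness and dental work as things to account for, but not radiotherapy or time since diagnosis.

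**Working it through.** **1. Outer window.** Take a woman 18 months after diagnosis who has completed chemotherapy.
- Section 4: she is within five years of completing chemotherapy, so she is eligible.
- Section 4.1: 18 months exceeds one year from diagnosis, so she is not eligible.

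The same holds for any woman one to five years past treatment, because the diagnosis that led to the treatment is older still. A recurrence might restart the one-year clock, but the text does not say so.

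**2. Recruitment at simulation.** At that visit radiotherapy has not started. Such a woman is not three months after chemotherapy and radiotherapy, whether the phrase means *within* or *at least* three months. She can still qualify through the reconstructive-surgery branch, or if the clause allowing additional treatment is read as overriding the timing. This conflict is therefore partial.

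**3. Chemotherapy.** Sections 3 and 4 require it to be completed. Sections 4.1 and 5.3.1 list it as allowed. Section 5.3.1 then rules it out during the study.

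**4. The plan's own power figure.** Protocol 8.2 and SAP C.5.1 state more than 90% power for d = 0.50 with 120 per arm. With two-sided alpha 0.05 (assumed, since the documents give none) and the normal approximation:

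Φ(0.50 × √(120/2) − 1.960) = Φ(3.873 − 1.960) = 0.972. The stated figure is reproduced.

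**5. Size of the noise.** Suppose a share p of women, equal in both arms, have a treatment-related shift of δ SD in their change score. With the other residual variance set to 1, the added variance is δ²p(1−p), and the effective sample is 240 / (1 + δ²p(1−p)). Neither δ nor p is in the documents, so both are varied.

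| δ (SD) | p | Added variance | Effective N |
|---|---|---|---|
| 0.5 | 0.2 | 0.25 × 0.16 = 4% | 240/1.04 = 231 |
| 0.5 | 0.5 | 0.25 × 0.25 = 6% | 240/1.0625 = 226 |
| 1 | 0.2 | 1 × 0.16 = 16% | 240/1.16 = 207 |
| 1 | 0.5 | 1 × 0.25 = 25% | 240/1.25 = 192 |

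**6. Power in the worst row.** With 96 per arm: Φ(0.50 × √48 − 1.960) = Φ(1.504) = 0.93. If the protocol's 15% attrition also fell after randomisation, 192 × 0.85 = 163.2, or 81.6 per arm: Φ(0.50 × √40.8 − 1.960) = Φ(1.234) = 0.89.

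**The case against.** The best defence is that 4.1 is the operative rule and section 4 is narrative. Sections 6.2.1 and 9.2 require screening against all inclusion and exclusion criteria, and section 4 limits the nurses' discretion to women who fit those criteria. This is a reasonable reading, but the protocol does not state it. The limit on discretion qualifies only recruitment at other stages, and section 4 argues for its five-year window, so that window does not look like a slip. If 4.1 does govern, the main recruitment visit would mostly supply women who fail it unless they enter by the surgery branch.

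A reader might infer that the two sections exclude each other altogether, so that no woman approached at simulation could be eligible. The documents do not support that. The surgery branch is a real alternative, and radiotherapy is listed as allowed in both 4.1 and 5.3.1. The numbering in 4.1 jumps from 2 to 4, so the clause on additional treatment may have been a criterion of its own.

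It also stands that the variance figures rest on assumption. At 0.5 SD they are small, and if d = 0.50 was standardised on the enrolled population, this spread may already be in its denominator.

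**Conclusion.** The point holds in a bounded form. The one-year and five-year windows contradict each other and nothing in the text resolves them. The three-month phrase is undefined and fits the simulation visit poorly, but that clash is partial. The statements on chemotherapy also need to be reconciled.

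The consequence is an undefined target population and some loss of precision: about 4% to 25% more residual variance, on assumed shifts of 0.5 to 1 SD in 20% to 50% of women. This is a range of scenarios, not an estimate.

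Two stronger conclusions might be drawn, and neither is supported. One is bias between arms: randomisation within sites protects the treatment contrast whichever rule a site applies. The other is failure of the power claim: in the worst scenario power for d = 0.50 is still 0.93, and falls just below 90%, to 0.89, only if 15% attrition is added. A blurred comparison of Jewish and Arab women would further require ethnicity to be unevenly spread over sites, which the documents do not show.

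**What to change.** - **One criterion.** The sponsor reconciles sections 4, 4.1 and 5.3.1 into a single entry criterion used word for word throughout. It should state time since diagnosis, time since last treatment (with *within* or *at least*), whether upcoming or ongoing radiotherapy is allowed, and the position on chemotherapy. The choice of windows is the sponsor's.
- **Recording.** Time since diagnosis and treatment phase are taken at the screening chart review that the schedule in 6.1 already contains.
- **Analysis.** Baseline treatment phase is added as a covariate in the mechanism and symptom models of SAP C.5.2.
- **Later radiotherapy.** The schedule in 6.1 marks chart review at screening only, so radiotherapy between T1 and T2 or T3 would need a short additional check.

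The cost is protocol and SAP wording, one or two fields on an existing form, and a small amount of extra chart work for the later check. If women have already been enrolled, the report should say which rule each site applied.
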